15.0 RESEARCH PARTICIPANT REGISTRATION AND RANDOMIZATION PROCEDURES

15.1 RESEARCH PARTICIPANT REGISTRATION

All patients must be centrally registered by the Data and Coordinating Center, at Memorial Sloan-Kettering Cancer Center. Registrations will be handled by the RSA at the Pediatrics Clinical Trials Office at MSKCC. The contact telephone number is [contact] or [contact] and the fax number is [contact]. Registrations will occur between 9:00 am and 5:00 pm Eastern Standard Time (EST), Monday through Friday and will include review of the signed consent form, HIPAA research authorization form, eligibility checklist, eligibility source documentation and Patient Enrollment form. The RSA will also verify, via a FAX copy, that the written informed consent is obtained and dated prior to subject entry on the study.

The participating sites must contact the Research Study Assistant (RSA) at the Data and Coordinating Center to reserve a slot on the protocol when a patient is being considered for a trial. To begin a registration the participating site must fax the signed consent form and HIPAA research authorization to the RSA within 48 hours of the patient signing consent. To complete the registration, the completed eligibility checklist, patient eligibility source documentation and the Patient Enrollment form must be faxed to the RSA at MSKCC prior to protocol treatment or any research tests. Registrations must be faxed to the Clinical Trials Office and the Research Study Assistant (RSA) at MSKCC will verify eligibility and complete the registration with the PPR Office.

Once eligibility has been established and the participant is registered, the participant will be assigned an MSKCC Clinical Research Database (CRDB) number (protocol participant number). This number is unique to the participant and must be written on all data and correspondence for the participant. This protocol participant number will be relayed back to study staff at the registering site via e-mail and will serve as the enrollment confirmation. The participating site must not begin treatment until receiving this email from the Data and Coordinating Center.

Written consent must be documented on the appropriate consent form and Research Authorization designated and approved by the Institutional Review Board at the institution at which the patient is enrolled. The POETIC Principal Investigators or consenting professionals at their institution

The registration procedure is summarized below.

Confirm eligibility as defined in the section entitled Criteria for Patient/Subject Eligibility.

Obtain informed consent, by following procedures defined in section entitled Informed Consent Procedures.

During the registration process registering individuals will be required to complete a protocol specific Eligibility Checklist.

All participants must be registered through the Protocol Participant Registration (PPR) Office at Memorial Sloan-Kettering Cancer Center. PPR is available Monday through Friday from 8:30am – 5:30pm at [contact]. The PPR fax numbers are [contact] and [contact]. Registrations can be phoned in or faxed. The completed signature page of the written consent/verbal script and a completed Eligibility Checklist must be faxed to PPR.

15.2 RANDOMIZATION

This study is not randomized.

16.0 DATA MANAGEMENT ISSUES

A Research Study Assistant (RSA) at the Memorial Sloan-Kettering Cancer Center will be assigned to the study. The responsibilities of the RSA include project compliance, data collection, abstraction and entry, data reporting, regulatory monitoring, problems and prioritization. In addition, coordination between the RSA and Research Staff at the participating POETIC institutions is necessary in order for a complete process. The Clinical Research Coordinator (CRC) will also be responsible for being the liaison among all staff involved including the principal investigators, attending physicians and nurses.

Case report forms will be drafted in a standard format and will be provided to each participating institution by the Data and Coordinating Center. Required study tools for each protocol including correlative studies, vital signs, drug administration and protocol evaluations will also be provided to each participating institution by the Data and Coordinating Center. Case report forms, study tools and source documentation are required to be submitted to the Data and Coordinating Center on a weekly basis.

The data collected for this study will be entered into a secure database by the MSKCC RSA. Data will be collected, stored, and monitored at an institutional level via the Clinical Research Database (CRDB) system. Data will be provided from CRDB to protocol-defined sponsors (CTEP, FDA, etc.) as required, through the Data Management Resource Division, a division of the Office of Clinical Research.

Source documentation will be available to support the computerized patient record and must be submitted with the case report forms and required study tools. Case report forms will not be considered source documentation. Variables that will be recorded include the patient's birth date, date of diagnosis, date of study entry and histologic diagnosis. The results of the pretreatment and end of therapy evaluations, including the extent of disease evaluation (history, physical examination and imaging studies), baseline laboratory values, renal and hepatic function, as defined per protocol, will be recorded. All study related treatment data and concomitant drugs will be recorded. The presence of toxicity at baseline, during and for 30 days after administration of the investigational agent will be monitored and recorded. The results of the extent of disease evaluation (history, physical examination and imaging studies) following each course of treatment will be recorded. The patient's disease status and last follow-up will be recorded. If disease progresses or recurs, the results of the repeat extent of disease evaluation will be recorded.

Research staff will be assigned at each POETIC center. Lead research personnel will be identified at each site. Their responsibilities will include maintaining file documentation of data for the clinical trial, pharmacokinetic or other biologic correlative study collection and analysis as outlined in this study, for each patient enrolled on study. They will also be responsible for maintaining a regulatory binder for each protocol. The designated research staff will also be responsible for submitting the data on a weekly basis by fax or mail to the RSA at MSKCC. Case report forms and required study tools along with supporting source documentation should be faxed or mailed to:

Pediatric Clinical Trials Office Memorial Sloan-Kettering Cancer Center [name] [contact] [contact]

The protocol will be conducted as a single research study effort and data from each participating institution will be included in the analysis of results.

[figure not shown]
The Protocol Chair will be responsible for the conduct of the study, and the monitoring of the progress and will review all case report forms from each participating institution.

Initial Protocol Submission

Prior to implementing this protocol at MSKCC, the protocol, informed consent form, HIPAA authorization and any other information pertaining to participants must be approved by the MSKCC IRB/PB. Prior to implementing this protocol at the participating centers, approval must be obtained from the participating center's Local IRB of Record.

The following documents must be provided to MSKCC before the participating site can be initiated and begin enrolling participants:

- Local IRB of Record approval(s) for the protocol, appendices, informed consent form and HIPAA authorization
- Local IRB of Record membership
- Local IRB of Record's Federal Wide Assurance number and OHRP Registration number
- Curriculum vitae and medical license for each investigator and consenting professional
- Documentation of Human Subject Research Certification and HIPAA training for investigators and key staff members
- Signed and dated FDA Related Forms 1572/1571 (if applicable)

• Lab Certifications and Reference Ranges for each lab listed on the 1572

Protocol Amendments/Status Changes

Each change to the protocol must be organized and documented by the Data and Coordinating Center. The Protocol Chair at the lead institution will submit the amendment locally for approval. After approval at the lead institution, the Data and Coordinating Center will distribute the amendment to the participating institutions, for approval by their local IRB within 60 days of the amendment date. The participating sites will ensure that documentation for all IRB approved amendments are sent to the Data and Coordinating Center and are maintained in the regulatory binder. This documentation will include the IRB approval letter referencing the protocol version date and amendment number, IRB approved protocol, IRB approved appendices and IRB approved consent forms.

The amendment will be written so that no other institution will need to reformat the information but can simply copy and distribute. An amendment memo as well as highlighted and clean copies of the protocol, appendices and consent forms will be distributed to the participating sites. The consent form will be a sample that may be edited in order to adhere to local IRB guidelines. The amendment must be submitted at each site to the IRB for review and approval before patients can be enrolled on the study and within 90 days of the amendment version date. The amendment number and version date will also be displayed on each amendment.

Additional IRB Correspondence

Annual re-approval

Annual re-approval from the participating center's Local IRB of Record must be submitted to MSKCC at the time re-approval is granted. The most current approved version of the consent form should also be submitted to MSKCC at that time. Failure to submit the re-approval will result in suspension of accrual privileges.

Deviations and Violations

If a deviation from the protocol is proposed for a potential or existing participant at a participating site, approval from the MSKCC IRB/PB is required prior to the action. Please be sure to inform the DCC as soon as possible to ensure IRB approval.

For protocol violations that are reported after they occur, the participating site should report to MSKCC as soon as possible. The MSKCC PI will in turn report the violation to the MSKCC IRB/PB.

Participating sites should report deviations and violations to the Local IRB of Record as they occur. Approvals/acknowledgments from the Local IRB of Record for protocol deviations and violations should be submitted to MSKCC as received.

Other correspondence

Participating sites should submit other correspondence to their local IRB of Record according to local guidelines, and submit copies of that correspondence to MSKCC.

16.1 QUALITY ASSURANCE

This will be a central responsibility of the Data and Coordinating Center and it will be achieved by frequent review, constant oversight and input from objective advisors. Each project will maintain a steering committee that will meet in conference call on a weekly basis to critically review the scientific progress of the clinical trial. The steering committee will include the principal investigators, research staff and the biostatistical support team under the direction of the lead biostatistician.

Monitoring visits will be conducted by the Clinical Research Coordinator (CRC) from the Data and Coordinating Center as needed. During this visit, the CRC will:

- Review regulatory binders for protocol documentation;
- Ensure that case report forms are source data verified according to the monitoring plan;
- Verify drug accountability is complete and accurate;
- Verify compliance to GCPs, ICH guidelines, FDA regulations, and applicable SOPs.

Internal audits will be conducted by the Data and Coordinating Center. Audits may be accomplished in one of two ways: (1) source documents and research records for selected patients are brought from participating sites to the Data and Coordinating Center for audit, or (2) selected patient records may be audited on-site at participating sites. Each site is responsible for having all source documents, research records, all IRB approval documents, Drug Accountability Record Forms, patient registration lists, response assessments scans, x-rays, etc. available for the audit.

16.2 DATA AND SAFETY MONITORING

The Data and Safety Monitoring Committee (DSMC) at Memorial Sloan-Kettering Cancer Center will be responsible for monitoring the data safety of the protocol. The DSMC meets quarterly, and will review data from respective trials on a semi-annual basis. A copy of the MSKCC Data and Safety Monitoring policy document has been distributed to local sites and is on file at the Data and Coordinating Center.

The Data and Safety Monitoring (DSM) Plans at Memorial Sloan-Kettering Cancer Center were approved by the National Cancer Institute in September 2001. The DSM Plans at MSKCC were established and are monitored by the Office of Clinical Research. The plans address the new policies set forth by the NCI in the document entitled "Policy of the National Cancer Institute for Data and Safety Monitoring of Clinical Trials" which can be found at: http://cancertrials.nci.nih.gov/clinicaltrials/conducting/dsm-guidelines. The MSKCC Data and Safety Monitoring Plans be found the Intranet can on **MSKCC** at: http://mskweb2.mskcc.org/irb/index.htm. The Data and Safety Monitoring Committee (DSMC) monitors all Phase I and II clinical trials and reports to the Research Council and Institutional Review Board.

17.0 PROTECTION OF HUMAN SUBJECTS

All of the patients on this study will be children, adolescents, and young adults. Patients of both sexes and all ethnic backgrounds are eligible for the study. Participation will be voluntary. The

IRB#: 09-014 A(7)

hypothesized potential benefits include superior event-free survival. Alternatives include external beam radiation therapy alone or in conjunction with other chemotherapy regimens, including, but not limited to (1) temozolomide, (2) vincristine and lomustine, or other investigational protocols.

Patients are responsible for all costs of their care including (but not limited to) physician visits, hospitalizations, medications (except for cetuximab), MRI scans, and laboratory work (except for the optional research biology studies performed on blood, tumor tissue and CSF). Cetuximab will be supplied by Bristol Myers-Squibb in collaboration with Imclone Systems Incorporated, via a research and development agreement. The costs of all research-only related studies will be covered by the study and participating institutions' research support.

Patient confidentiality will be protected, but records may be reviewed by appropriate staff of the Memorial Sloan-Kettering Cancer Center, the participating institutions, and representatives from the FDA, Bristol Myers-Squibb, and Imclone Systems Incorporated.

17.1 PRIVACY

All institutional, local, federal, FDA, and NCI requirements for human subjects research must be met. This study will be carried out in compliance with the regulations of the Health Insurance Portability and Accountability Act (HIPAA). Each participating institution will have an appropriate assurance on file with the Office for Human Research Protection (OHRP), NIH. The Data and Coordinating Center is responsible for assuring that each participating institution has an OHRP assurance and must maintain copies of IRB approvals from each participating site. The Data and Coordinating Center is responsible for assuring that IRB approval has been obtained at each participating site prior to the first patient registration from that site.

The risks and benefits of participation in this study will be reviewed with the patient and/or parent/legal guardian.

Enrollment on this study is on a voluntary basis and every effort will be made to maintain privacy and confidentiality. The patient's records will be confidential. Only authorized individuals or agencies may inspect the records. No identifying information will be used in reports or publications resulting from this study.

17.2 SERIOUS ADVERSE EVENT (SAE) REPORTING

The Protocol Chair is responsible for monitoring the safety of patients who enroll in the study. All AEs and SAEs occurring after any administration of the study drug regardless of drug attribution will be followed to the end of the study including 30 days after the last administration of study drug, as well as any SAEs designated possibly, probably or definitely related to treatment that occur greater than 30 days.

The descriptions and grading scales found in the revised NCI Common Terminology Criteria for Adverse Events (CTCAE) version 3.0 will be used for adverse event and serious adverse event reporting. All participating sites should have access to a copy of the CTCAE version 3.0. A copy of the CTCAE version 3.0 can be downloaded from the CTEP web site (http://ctep.cancer.gov/reporting/ctc.html).

The Protocol Chair is required to report all adverse events that occur during the clinical study starting with the first dose of study drug throughout 30 days of stopping the investigational agent, must be reported to the appropriate protocol-defined study sponsors. Serious adverse events must be reported either by telephone or in person to the Protocol Chair, Data and Coordinating Center and local IRB within 24 hours of knowledge of their occurrence. A written SAE report including source documentation must be sent to the Protocol Chairman and Data and Coordinating Center within another 3 calendar days, using the Serious Adverse Event case report form.

Additionally, the Protocol Chair is responsible for submitting follow-up reports for all SAEs regarding the patient's subsequent course until the SAE has resolved or until the patient's condition stabilizes (in the case of persistent impairment), or the patient dies.

A serious adverse event (SAE) is any adverse drug experience that occurs at any dose that results in any of the following outcomes:

- Death
- Life-threatening adverse drug experience
- Requires inpatient hospitalization or prolongation of existing hospitalization
- For the purpose of this study, hospitalizations for protocol-scheduled procedures, blood product transfusions, or for social reasons (ie, awaiting transport home) will not be considered SAEs
- Persistent or significant disability/incapacity
- A congenital anomaly/birth defect
- Requires medical or surgical intervention to prevent one of the outcomes listed above

Reporting Requirements for Adverse Events That Occur on Treatment and Within 30 Days¹ of the Last Dose of Study Drug (Please see section 17.2.1 for exception to the table)

	Grade 1	Grade 2		Grade 2		Grade 3		Grade 3		Grades 4 & 5
	out	Unexpected		Expected		Unexpected		Expected		
with out		With Hospitali	without Hospitaliz ation	With Hospitali zation	Without Hospitaliza tion	With Hospitali zation	Without Hospitali zation	With Hospitalizat ion	Without Hospitaliz ation	Unexpected and Expected
Unrelated Unlikely	Not Required	SAE Report Required	Not Required	SAE Report Required	Not Required	SAE Report Required	Not Required	SAE Report Required	Not Required	SAE Report Required
Possible Probable Definite	Not Required	SAE Report Required	SAE Report Required	SAE Report Required	Not Required	SAE Report Required	SAE Report Required	SAE Report Required	Not Required	SAE Report Required
 Adverse events with attribution of possible, probable, or definite that occur greater than 30 days after the last dose of study treatment require an SAE report as follows: Grade 3 unexpected events with hospitalization or prolongation of hospitalization 										

Grade 4 unexpected events

Grade 5 expected events and unexpected events

Initial notification for all SAEs must include:

- Grade of event
- Date of event
- A brief description of the event
- Attribution to the investigational agent
- Patient Status

Relationship of any adverse event to study drug should use the following criteria:

[figure not shown]
- Definite The adverse event *is clearly related* to
- Probable The adverse event *is likely related* to
- Possible The adverse event *may be related* to
- Unlikely The adverse event *is doubtfully related* to
- Unrelated The adverse event is clearly NOT related to

SAEs must be reported within 24 hours by phone or e-mail to:

- Data and Coordinating Center
- Lead Principal Investigator of the protocol / Protocol Chair
- Local IRB

SAE contact information for the Data and Coordinating Center is listed below:

Memorial Sloan-Kettering Cancer Center Pediatric Clinical Trials Office [name] [contact] [contact]

Contact information for the Primary Investigator is listed below:

Primary Investigator

[name] Memorial Sloan-Kettering Cancer Center [name] [contact] [contact] E-mail: [contact]

In the event of an AE, appropriate medical and supportive care will be administered. All efforts will be made to minimize the side effects and to support the patient until the toxicity resolves.

- Adverse events classified as "serious" require expeditious handling and reporting to BMS to comply with regulatory requirements.
- All serious AEs whether related or unrelated to investigational product, must be immediately reported to the Data and Coordinating Center by confirmed facsimile transmission. If only limited information is initially available, follow-up reports are required. The original SAE form must be kept on file at the study site.

All SAEs should simultaneously be faxed or emailed to Data and Coordinating Center (see above) who will submit the information to Bristol-Myers Squibb at:

Global Pharmacovigilance & Epidemiology Bristol-Myers Squibb Company [contact] Email: [contact]

- Collection of complete information concerning SAEs is extremely important. Full descriptions of each event will be followed by BMS. Thus, follow-up information which becomes available as the SAE evolves, as well as supporting documentation (e.g., hospital discharge summaries and autopsy reports), should be collected subsequently, if not available at the time of the initial report, and immediately sent using the same procedure as the initial SAE report.
- An overdose is defined as the accidental or intentional ingestion of any dose of a product that is considered both excessive and medically important. For reporting purposes, BMS considers an overdose, regardless of adverse outcome, as an important medical event (see Serious Adverse Events).
- In BMS supported trials, all SAEs must be collected which occur within 30 days of discontinuation of dosing or completion of the patient's participation in the study if the last scheduled visit occurs at a later time. In addition, the Investigator should notify BMS of any

SAE that may occur after this time period which they believe to be certainly, probably or possibly related to investigational product.

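### The SAE reporting table and section 17.2.1 contradict the outcome-based SAE definition in 17.2: they waive the report with no exception for disability, birth defect or preventive intervention

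*Combined protocol and SAP*

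**What the plan says.** Section 17.2 opens its definition with "A serious adverse event (SAE) is any adverse drug experience that occurs at any dose that results in any of the following outcomes". It then lists death, threat to life, inpatient hospitalization (with some exclusions), "Persistent or significant disability/incapacity", "A congenital anomaly/birth defect" and "Requires medical or surgical intervention to prevent one of the outcomes listed above". Grade, expectedness and attribution play no part. SAEs go to the Protocol Chair, the Data and Coordinating Center and the local IRB within 24 hours. Later in the section, under reporting to the drug supplier, the duty is repeated without condition: "All serious AEs whether related or unrelated to investigational product, must be immediately reported to the Data and Coordinating Center by confirmed facsimile transmission".

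The table headed "Reporting Requirements for Adverse Events That Occur on Treatment and Within 30 Days" sorts events by grade, expectedness, hospitalization and attribution, and marks each cell as needing an SAE report or not. Its title adds "Please see section 17.2.1 for exception to the table". Section 17.2.1 lists expected admissions that are not SAEs. It then exempts toxicities of grade 3 or 4 that do not threaten life and are plainly due to radiation or chemotherapy, and brings back only life-threatening events.

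On overdose, 17.2 says "An overdose is defined as the accidental or intentional ingestion of any dose of a product that is considered both excessive and medically important". The supplier treats an overdose as an important medical event whatever follows from it.

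**The concern.** The definition and the table can classify one event in opposite ways. Three of the listed outcomes (disability or incapacity, birth defect, and intervention to prevent a listed outcome) need neither death, nor threat to life, nor an admission. The table has no row, column or footnote for them. Whether such an event produces a 24-hour notice, and onward notice to the supplier, then depends on which part of the section a site uses. Section 3.6 says that cetuximab with external beam radiation had not been studied in pediatric patients, so prompt and uniform notice matters here.

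The overdose rule has a smaller defect. It speaks of *ingestion*, while sections 5.2 and 9.1.2 give irinotecan and cetuximab intravenously.

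**Working it through.** No formula applies. The check is a count of table cells and a side-by-side reading.

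**1. The table.** It has 10 columns and 2 attribution rows, so 20 cells. The cells for grade 2–3 events without hospitalization read:

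| Event, no hospitalization | Unrelated/unlikely | Possible/probable/definite |
|---|---|---|
| Grade 2, unexpected | waived | report |
| Grade 2, expected | waived | waived |
| Grade 3, unexpected | waived | report |
| Grade 3, expected | waived | waived |
| Waived | 4 of 4 | 2 of 4 |

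That is 4 + 2 = 6 of 8 waived. The 2 grade 1 cells are waived as well, giving 6 + 2 = 8 of 20. The other 12 require a report: 8 hospitalized cells, 2 grade 4–5 cells and the 2 shown above.

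**2. Which serious outcomes can fall in a waived cell.** Hospitalization has its own columns. Death and threat to life should fall under grades 4 and 5; this is an assumption, because the documents reproduce only the rash grades of CTCAE v3.0 (section 10.3, Table 1). The other three outcomes have no place in the table. An event with one of them, graded 1 to 3 and managed without admission, is serious under 17.2. It is waived by the table unless it is unexpected, related and of grade 2 or 3.

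**3. What 17.2.1 adds.** It is the only exception the table cites, and it removes events. Take a disabling grade 4 event that does not threaten life and is plainly due to radiation. The table's grade 4–5 cell requires a report, 17.2.1 withdraws it, and the clause restoring life-threatening events does not bring it back. The gap therefore does not stop at grade 3.

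**4. After 30 days.** The table's footnote asks for reports of related events only if they are grade 3, unexpected and hospitalized; grade 4 and unexpected; or grade 5. The supplier paragraph asks the investigator to notify any SAE in that period believed at least possibly related. An expected, related, disabling late event that is not fatal meets the second rule and not the first.

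**5. Overdose.** Read literally, an infusion overdose is not an ingestion. If it causes a listed outcome, it is an SAE under the definition anyway. What drops out is the infusion overdose without such an outcome. The cross-reference to serious adverse events does not help, because the 17.2 list has no category for important medical events and the table has no cell for an overdose without an adverse event.

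**6. What is lost.** Section 11.0 records toxicities of grades 1–4 in both phases until 30 days after the last cetuximab dose. Section 17.2.1 sends events that are not expedited into routine data, and section 16.0 has case report forms submitted weekly. Within that window, the loss is the expedited report and not the record of the event.

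**The case against.** The strongest answer is that 17.2 requires SAEs within 24 hours, and its supplier paragraph requires all serious events immediately, without making either duty depend on the table. A site that reads the whole section would report correctly. That stands, and it makes this a contradiction in the instructions and not a certain loss of events.

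Three stronger readings are tempting and are not supported.

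- A reader might infer that serious events would go unrecorded. The routine recording in sections 11.0, 16.0 and 17.2.1 rules that out for events within 30 days of the last cetuximab dose.
- A reader might infer that the safety objective (primary objective 2) or the stopping rule is compromised. Section 14.2 counts non-hematological toxicity of grade 4 and above, with listed exceptions, that has not settled to grade 2 or below in 7 days. It does not use SAE status, and nothing in section 14 analyzes SAE counts.
- A reader might point to hearing loss and neurocognitive dysfunction, named in section 11.1, as the events at risk. Section 11.1 lists them as late effects without onset times. Those arising more than 30 days after the last dose fall under the footnote and not under the table's cells, and where they are plainly due to radiation, 17.2.1 applies. They do not show that the waived cells would often be used.

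It can also be said that no sensible site would read the overdose rule as excluding infusions. That is fair, and the wording point is minor.

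Finally, an override covering every outcome in 17.2 would pull in admissions, such as those for fever with neutropenia, that 17.2.1 deliberately excludes. That objection is right and limits the fix.

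**Conclusion.** The contradiction is real and lies within one section and its subsection. The table waives the SAE report in 6 of 8 non-hospitalized grade 2–3 cells and both grade 1 cells, with no exception for three outcomes that make an event serious. Section 17.2.1 extends the gap to some grade 4 events. The consequence is a missing 24-hour report from a site that applies the table or 17.2.1 literally. The toxicity record is kept, and no endpoint or stopping decision is affected.

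This rests on the cell pattern as it can be read; the table's header is partly broken in the copy used, but the entries are clear. How often a disabling event would be graded 3 or lower cannot be settled from the documents, so the number of affected reports is unknown.

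**What to change.** Add one line both to the table and to 17.2.1, for example: *An SAE report is required for any event whose outcome is one of the last three listed in 17.2 (disability or incapacity, birth defect, or intervention to prevent a listed outcome), whatever its grade, expectedness, attribution or hospitalization. The hospitalization exclusions in 17.2 and 17.2.1 are unchanged.* Because hospitalization is itself a listed outcome, the line should make clear that outpatient treatment to avert an excluded admission does not trigger a report.

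State whether the line also governs the beyond-30-day footnote, and reconcile that footnote with the late-SAE sentence in the supplier paragraph.

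As a minor correction, replace *ingestion* in the overdose definition with *administration by any route*, and say that an overdose is reported as an SAE even without an adverse event.

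The cost is a short amendment and some extra SAE reports, whose number the documents do not allow to be estimated.
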